**Describe how and where PHI will be destroyed following the completion of the study:**

Not applicable. No identifiable data will ever be shared by the study team with personnel outside of the approved study staff. Any data shared with external laboratories or other researchers will be de-identified. All the findings in this study will be de-identified or reported at a group level or in aggregate with no risk of identifying individual participants.

**Will subjects be able to request that their information be removed from the data bank?**

Yes. However, it may not be possible to withdraw or delete materials or data in the event that they have already been shared with other researchers.

**Costs:**

There will be no direct cost to participants to participate in this study. All clinical, professional, diagnostic and laboratory services related to the study will be provided at no cost to participants. However, participants will be responsible for their phone service provider's standard charges as they apply to any study-related phone calls.

**Compensation:**

	Intake	CPT Day 1	1- Week Post	2- Week Post	1- Month Post	3- Month Post	Total
Completion of Measures & Provision of Saliva Samples*	\$20	N/A	\$40	\$15	\$40	\$50	\$165
Provision of Optional Fecal Sample	\$10	\$ 10	\$10	N/A	\$10	\$10	\$50
Completion of Optional Semi-Structured Interview			\$15				\$15
Total Compensation Possible	\$30	\$10	\$65	\$15	\$50	\$60	\$230

\* Provision of saliva samples not available to participants who opt to participate via telephone/video.

## Data analysis

We utilized Bayesian longitudinal mixed models to examine change over the course of 1-week massed virtual CPT. The use of mixed-effects models is particularly appropriate for longitudinal analysis due to their ability to account for within-subject clustering and correlations in individual change across measurements. The Bayesian approach also allows for the incorporation of prior knowledge and results as well as for the intuitive and substantive assessment of uncertainty. Additionally, as has been noted with regularity elsewhere, Bayesian methods may be uniquely suited to estimation with small sample sizes (Depaoli & van de Schoot, [2017](#); Dunson, [2001](#)), such as the present study, although this benefit may be contingent upon careful selection of informative priors (McNeish, [2016](#)). Here, weakly informative priors for time parameters were based on our prior treatment outcomes in both 3-week and 2-week CPT-based ITPs (Held et al., *in press*), though sensitivity analyses were conducted to examine the robustness of outcomes relative to various prior selections. Models initially examined the effects of time, as well as age and sex, which were given very vague priors (e.g.,  $N \sim [0, 5]$ ) for age) due to past massed-treatment results indicating a lack of association with ITP outcomes (Held et al., *in press*). Small cell sizes obviated the examination of other covariates, such as race and ethnicity, although these variables have not been shown to predict treatment outcomes in prior studies. Simulation-based power analyses based on prior effect sizes for PTSD and depression reduction (Held et al., *in press*) suggested that over 90% power for detecting changes in these outcomes should be attainable with over 15 participants.

To ensure the viability of priors, prior predictive checks were conducted across 1,000 simulated datasets to ensure the alignment of priors with appropriate values. Hamiltonian Markov chain Monte Carlo (MCMC) was utilized for sampling from the posterior via the No-U-Turn Sampler algorithm (NUTS). We utilized five chains, each with 1,000 burn-in iterations and 5,000 inference iterations. Posterior distributions were summarized via 94% highest density intervals (HDIs), which report the most credible values from the posterior distribution, as well as medians and means. Model checking involved the examination of trace, autocorrelation, and divergence plots assessing the posterior, as well as visual posterior predictive checks of mean, median, variance, and skewness parameters.

We also explored maintenance of gains by comparing 1-week posttreatment symptom severity (i.e., CAPS-5, PCL-5, and PHQ-9) to both 1- and 3-month follow-up time points. We utilized noninferiority tests to assess the probability that 1- and 3-month follow-up severity scores were not inferior to those recorded at 1-week

posttreatment. A recently developed Bayes actor approach (van Ravenzwaaij et al., [2019](#)) was utilized here, which allowed for intuitive interpretations of noninferiority by assessing the probability that the follow-up severity measurement can be considered noninferior to the posttreatment measurement relative to the probability that the initial postprogram measurement is superior. This approach was modified to accommodate the repeated-measures structure of the comparisons of interest. We chose conservative noninferiority intervals of 5 points for the PCL-5 and CAPS-5 and 3 points for the PHQ-9.

Bayesian linear mixed models were also explored, including follow-up timepoints. As expected, the linear, PCL-5:  $B = -0.37$ , HDI  $[-0.72, -0.01]$ ; PHQ:  $B = -0.18$ , HDI  $[-0.34, -0.02]$ , and quadratic slope components, PCL-5:  $B = 0.004$ , HDI  $[0.0004, 0.007]$ ; PHQ-9:  $B = 0.001$ , HDI  $[0.003, 0.002]$ , were clear given the deceleration of outcome reduction over follow-up time points. These results are not reported here in detail due to consistency with reported results as well as our interest in modeling the degree of massed CPT change and post hoc illustrations of noninferiority of follow-up points compared to outcomes immediately following the treatment. Bayesian linear mixed models and model checks were explored using PYMC3 in Python (Version 3.9.), and noninferiority tests and figures were conducted using R (Version 4.1.1.)

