## **Examining Changes in Microbiota over the Course of PTSD Treatment**

The overall goals of this project are to evaluate the use of 5-day intensively-delivered Cognitive Processing Therapy to treat PTSD and to determine the associations between the microbiome, salivary cytokines, and the presence of and recovery from PTSD. Specifically, this study is designed to 1) determine whether individual Cognitive Processing Therapy (CPT) delivered twice per day over 5 consecutive days (CPT-5) is tolerable, acceptable, and effective in reducing PTSD symptoms, 2) determine the microbial signatures associated with PTSD, 3) evaluate whether the abundance and composition of microbiota and salivary cytokine levels change over the course of PTSD treatment, and 4) examine whether changes in microbial signatures are associated with changes in cytokine levels.

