**Research Plan:**

**Study Population:**

Trauma-exposed individuals will be recruited from the Rush Department of Psychiatry, Department of Behavioral Sciences, the Rush newsletters, the Rush website, Road Home Program: Center for Veterans and their Families, other Rush clinics, and postings to Rush/Road Home Program social media pages and website. Local first responders will also be recruited. Recruitment flyers will be posted in waiting areas in the Rush Departments of Psychiatry and

Behavioral Sciences. Approximately 200 individuals will be screened, anticipating that 40% of those screening positive on the phone and expressing interest in the study will be eligible and willing to participate (~40% of 200 screened = 80 participants). We plan to enroll at least 80 trauma-exposed individuals who meet the diagnostic criteria for PTSD, as assessed by a gold standard clinician-administered PTSD assessment, for the single-arm, open-label trial.

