#### ***Intensive Week-Long Cognitive Processing Therapy (CPT):***

The eligible individuals will undergo a course of 1-week-long Cognitive Processing Therapy (CPT-5). CPT-5 will be delivered twice per day over the course of five business days (Monday through Friday; 10 sessions total) at approved study sites or via the HIPAA compliant platform.

Each 50 minute session will closely follow the CPT protocol and will be conducted by either [name], other doctoral-level psychologists, postdoctoral fellows, or other Master's level (or higher) clinicians who have received the official two-day CPT training and who are not involved in study assessments. All CPT sessions will be audio and/or video recorded and an independent fidelity rater with experience in the treatment will randomly select and review 20% of all therapy audio recordings to ensure that the intervention is provided with fidelity, which will be defined as 80% or more of the maximum possible score on the official CPT fidelity rating scales. CPT worksheets and homework assignments may be collected and copied for research purposes. Individuals with telephone/video sessions will have the option to complete electronic versions of CPT worksheets and to upload them to a secure folder accessible only by the individual and study staff.

Changes in PTSD severity and other relevant symptoms will be assessed before, during, and after the course of CPT using well-validated clinician-administered, self-report, and computerized assessments. Completion of assessments may take between 20 minutes for self-report measures and 90 minutes for combined self-report, computer-based, and clinician-administered assessments. Fecal- and oral-derived microbiota as well as salivary cytokines will also be assessed at various pre-treatment, post-treatment, and follow-up time points to determine whether the microbiome and cytokine levels change over the course of CPT. Participants will have the option to opt out of providing these biological samples and still receive CPT-5. Participants completing telephone/video sessions can provide optional fecal samples and will complete brief computerized assessments, but will not provide saliva samples.

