**Note:**

**CAPS-5** = Clinician Administered PTSD Scale for DSM-5; **C-SSRS** = Columbia-Suicide Severity Rating Scale; **DIAMOND** = Structured Diagnostic Interview for Anxiety, Mood, OCD and related Neuropsychiatric Disorders; **Ohio TBI Screen** = Ohio Traumatic Brain Injury Screen; **PCL-5** = PTSD Checklist- Identified Patient Version; **PHQ-9** = Patient Health Questionnaire; **GAD-7** = Generalized Anxiety Disorder – 7-item; **PTCI** = Post-Traumatic Cognitions Inventory; **ADL** = Activities of Daily Living; **AUDIT-C** = Alcohol Use Disorders Identification Test; **DAST-10** = Drug Abuse Screening Test; **CD-RISC-10** = Connor-Davidson Resilience Scale – 10 items; **PROMIS-SF-8** = Patient-Reported Outcomes Measurement Information System Satisfaction with Participation in Social Roles Short Form; **PROMIS-SD-SF** = Patient-Reported Outcomes Measurement Information System Sleep Disturbance Short Form; **PROMIS-SRI-SF** = Patient-Reported Outcomes Measurement Information System

Sleep-Related Impairment Short Form; **RAND-12+** = The Veterans Rand 12-Item Health Survey; **FFQ** = VioScreen Food Frequency Questionnaire

\*Fecal collection will take place within one day of the assessment and prior to the following assessment. The CPT-5 Day 1 sample should ideally be collected on Sunday, one day before the first session, or as soon as possible after. For participants who did not complete the intensive CPT, follow-up intervals will follow the same schedule as for individuals who complete treatment.

†These assessments will not be administered to participants who opt to participate via telephone/video.

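### Does the SAP's effectiveness analysis cover only virtual delivery, when the trial also treats people in person?

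*SAP*

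**What the plan says.** The SAP's Data analysis section introduces the effectiveness model with this sentence: "We utilized Bayesian longitudinal mixed models to examine change over the course of 1-week massed virtual CPT". The model terms it names are time, age and sex; delivery mode is not among them. It counts the trial among small samples ("such as the present study, although this benefit may be contingent upon careful selection of informative priors"). Its simulation-based power statement says that more than 90% power "should be attainable with over 15 participants". It gives no analysed number, in total or by mode, and does not say how in-person participants are handled. Its last paragraph refers to the treatment again without naming a mode.

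The protocol is broader. Its opening statement of goals asks whether individual CPT "delivered twice per day over 5 consecutive days (CPT-5) is tolerable, acceptable, and effective in reducing PTSD symptoms", with no mode named. The section on the week-long treatment allows delivery "at approved study sites or via the HIPAA compliant platform". Under Study Population: "We plan to enroll at least 80 trauma-exposed individuals who meet the diagnostic criteria for PTSD". That target is for one open-label arm and is not divided by mode. The note under the assessment table shows that remote participation is the participant's choice: "These assessments will not be administered to participants who opt to participate via telephone/video".

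**The concern.** Set beside the protocol, the adjective *virtual* reads like a restriction of the analysis set. The first aim is about CPT-5 however it is delivered. If in-person participants were treated but left out of the model, the reported change would describe a group that chose its own mode, and it would not by itself support a conclusion about CPT-5 in general. In a single-arm trial with no comparator, the meaning of the estimate depends heavily on who is analysed.

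Two other phrases add to the doubt. Calling the study small, and citing power for a number just above 15, sit awkwardly beside a target of at least 80. Three readings are possible: *virtual* loosely describes the whole sample; only a remote subset was modelled; or the text reports an early or partial cohort. The SAP text available does not say which applies.

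**Working it through.** **1. The planned number.** Study Population screens about 200 and expects 40% to be eligible and willing: 0.40 × 200 = 80. The figure reproduces. It is an enrolment target, not an analysed number, and it has no split by mode.

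**2. What the power statement shows about sample size.** It comes from simulation, and its effect size, SD, alpha and sidedness are not given, so it cannot be reproduced. As a bounded check, assume a paired pre-post test at two-sided alpha 0.05. The standardised change needed for 90% power is, by normal approximation, d = (1.960 + 1.282)/√n.

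| n | d, normal approximation | d, noncentral t |
|---|---|---|
| 16 | 3.242/4.000 = 0.81 | 0.87 |
| 80 | 3.242/8.944 = 0.36 | 0.37 |

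With d = 1.0, the t-based power is 0.96 at n = 16 and 1.00 to three decimals at n = 80. The statement sets a size above which power is adequate. A sample of 80 satisfies it as well as a sample of 16, so it is no evidence that about 16 people were analysed.

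**3. The readings side by side.**

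| Reading | What follows |
|---|---|
| *Virtual* loosely describes everyone analysed | The model addresses the first aim; one word is loose |
| Only remote participants were modelled | The result is valid for remote delivery, the scope its own sentence states |
| A partial cohort is reported | Fewer people give a wider interval, which the posterior summary shows; the stated scope is still virtual |

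None of these makes the model wrong for the people it was fitted to. The missing mode term does not change that. If everyone was remote there is nothing to adjust for. If the sample was mixed, average change over all treated participants is what the first aim asks for.

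**4. Size of a possible shift.** Let v of 80 participants be remote, with mean changes M_v (remote) and M_p (in person). The mean over all is (v/80)·M_v + ((80 − v)/80)·M_p, so

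M_v − M_all = ((80 − v)/80) × (M_v − M_p).

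| v (assumed) | Shift per 1-point difference between modes |
|---|---|
| 80 | 0 |
| 72 | 8/80 = 0.10 |
| 40 | 40/80 = 0.50 |
| 16 | 64/80 = 0.80 |

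The documents give neither v nor the difference between modes. The table is an identity over assumed splits. It does not demonstrate bias.

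**5. Two passages that do not decide the matter.** The SAP's last paragraph drops the adjective, which is ordinary shorthand on second mention and not a contradiction. The protocol's note "For participants who did not complete the intensive CPT, follow-up intervals will follow the same schedule as for individuals who complete treatment" concerns the follow-up of people who stop treatment early and says nothing about mode.

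**The case for a change.** The strongest case for a change rests on the protocol's other aims. Remote participants give no saliva, so the cytokine part of the third aim, and the fourth aim, depend on people seen in person. The protocol also describes in-person intake first and telephone/video as the alternative. The design therefore expects in-person participants, and *virtual* cannot be assumed to be shorthand for the whole trial. With no analysed number by mode, a reader of the SAP alone cannot tell how far the effectiveness result extends, and a sentence with a small table would settle it.

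Much of this stands. The mismatch in wording is real, and the SAP text available does not resolve it. The argument stops short of a fault in the analysis, however. A design that expects in-person participants does not show that any were treated, still less that any were dropped. The SAP text is written in the past tense, already gives estimates, and refers to results reported outside it. It is part of a fuller account, and some SAP text ahead of this section is not available, so a description of the sample may exist. Nor does the section claim anything about in-person delivery or CPT-5 in general; its stated scope is no wider than the sentence that opens it. Finally, because results are already reported, an analysis set defined now would be post hoc and would not gain the protection of pre-specification.

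**Conclusion.** No change to the plan is needed. This is missing description that analysts fill as a matter of course: a report of a single-arm trial gives its participant flow and can state the number analysed by mode. If only remote participants were modelled, the conclusion reads as one about remote delivery, as the SAP sentence already implies.

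The numerical effect cannot be determined from the documents. It is zero if no one was treated in person or if the modes do not differ; otherwise it is the in-person share times the difference between modes, both unknown. The conclusion rests on two things: the documents show no exclusion of in-person participants, and the SAP draws no conclusion beyond the mode it names. Evidence that in-person participants were treated and left out, while the result was presented as covering CPT-5 in either mode, would reopen the point.

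### Maintenance of gains is judged by separate two-visit Bayes factor comparisons with no stated rule for missing follow-up scores; a visit contrast from a mixed model would be safer

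*SAP*

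**What the plan says.** The SAP has a single section, Data analysis. It describes the maintenance question as "comparing 1-week posttreatment symptom severity (i.e., CAPS-5, PCL-5, and PHQ-9) to both 1- and 3-month follow-up time points", which makes three outcomes by two visits, or six comparisons. On margins it states: "We chose conservative noninferiority intervals of 5 points for the PCL-5 and CAPS-5 and 3 points for the PHQ-9". The method is a published Bayes factor approach, and the only words on within-person correlation are "This approach was modified to accommodate the repeated-measures structure of the comparisons of interest". The modification itself is not described.

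The mixed models were fitted in Python, whereas "noninferiority tests and figures were conducted using R". The SAP also reports that "Bayesian linear mixed models were also explored, including follow-up timepoints". It prints linear and quadratic slopes for PCL-5 and PHQ-9 and none for CAPS-5, and adds "These results are not reported here in detail due to consistency with reported results". It calls the noninferiority work "post hoc illustrations of noninferiority of follow-up points compared to outcomes immediately following the treatment".

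The assessment schedule in the protocol (Measures) places PCL-5 and PHQ-9 at 1 week, 2 weeks, 1 month and 3 months after treatment, and CAPS-5 at 1 week, 1 month and 3 months. The notes to that schedule keep people who stop treatment on the same follow-up calendar. Neither document gives a missing-data rule, an expected dropout rate or a count of pairs for these comparisons.

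**The concern.** A comparison of two visits made outside the longitudinal model most naturally uses people with a score at both. Someone seen at 1 week, 2 weeks and 1 month but not at 3 months would then add nothing to the 3-month comparison, even if the 1-month score already showed symptoms returning.

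In a noninferiority question this matters more than usual. If people who worsen are less likely to attend, those who remain show too little mean worsening, and the error runs towards the favourable conclusion that gains were kept. The SAP already fits models that could use the intermediate scores, but it does not draw the maintenance conclusion from them.

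**Working it through.** **1. The plan's own figures.** There is no power or error figure for noninferiority to reproduce. The one sample-size statement (over 90% power with more than 15 participants) concerns change during treatment and comes without an effect size. A paired t-test at two-sided 5% would need a standardised change of about 0.87 at n=16 to match it. That has no bearing on this point.

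**2. Inputs.** From the documents: the 5-point PCL-5 margin, the visit schedule and planned enrolment of at least 80. Assumed, because the documents give none of them:
- SD 15 at each visit.
- Correlations of 0.7 (1 week with 1 month), 0.8 (1 month with 3 months) and 0.7 (1 week with 3 months).
- True worsening of 2.5 points at 1 month and 5 points (exactly the margin) at 3 months.
- 20% or 30% missing at 3 months, with the odds of being missing multiplied by 1.6 or 2.7 per 10 points of worsening at 1 month.

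**3. Size of the shift.** Let D1 and D3 be the changes from 1 week to 1 month and to 3 months.
- Var(D1) = 2 × 15² × (1 − 0.7) = 135.
- Cov(D1, D3) = 15² × (0.8 − 0.7 − 0.7 + 1) = 90.
- For mild selection, the complete-pair mean of D3 is about 5 − p × β × Cov(D1, D3), where p is the missing fraction and β = ln(odds ratio)/10.
- With p = 0.2 and odds ratio 1.6, β = 0.0470, so the mean is 5 − 0.2 × 0.0470 × 90 = 4.15.

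| Missing | Odds ratio per 10 points | Approximation | Simulated complete-pair mean, n=80 | False noninferiority, nominal 5%, n=80 |
|---|---|---|---|---|
| 20% | 1.6 | 4.15 | 4.14 | 14.4% |
| 20% | 2.7 | 3.21 | 3.46 | 28.6% |
| 30% | 1.6 | 3.73 | 3.76 | 20.4% |
| 30% | 2.7 | 2.32 | 2.82 | 40.6% |

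Each simulated setting has 2,000 trials. The approximation overstates the shift when selection is strong, so the simulated column is the one to use. At n=20, false noninferiority is 8-17%. An estimate that also uses the 1-month score returns 4.97 to 5.03 at n=80.

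**4. Sensitivity to the correlations.** With all three equal to 0.7, Cov(D1, D3) = 225 × 0.3 = 67.5; with all equal to 0.8 it is 225 × 0.2 = 45. The bias shrinks accordingly: the complete-pair mean is 3.4 to 4.6, with false noninferiority of 9-29% at n=80. Adding a pattern of 0.8 between adjacent visits and 0.7 from 1 week to 3 months, the range reaches 30% at n=80 and is 7-13% at n=20. With dropout unrelated to worsening (β = 0), the mean is 5 and the error about 5%.

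**5. A Bayes factor version.** Assume a Cauchy prior of scale 0.707, a threshold of 3, SD of change 12, and 20% missing that depends on the unseen 3-month change (odds ratio 2 or 4 per SD). At n=24 the chance of favouring noninferiority at the margin is about 0.16-0.20 with full data, against 0.39 or 0.57 with complete pairs (400 runs; error about ±0.05). The SAP gives neither prior nor threshold, so this shows direction only.

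**6. What a mixed model does not cure.** When dropout depends on the unseen 3-month change, the estimate using the intermediate score recovers only 3.1 to 4.3 of the 5 points under the step 2 correlations, against 1.7 to 3.7 for complete pairs. Under the step 5 assumptions, with 20-30% missing, it recovers 2.8 to 4.2.

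**The case against.** A reader might infer that the test is known to discard everyone without a follow-up score. The documents do not say so. The SAP mentions an adaptation for repeated measures and stops there; paired differences and exclusions are not mentioned, and using R proves nothing, since R also fits mixed models. Complete pairs is the likely reading, not an established one.

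A reader might also infer that the reported maintenance result is inflated. That is not supported either. No attrition is documented, and several features work against it: people who stop treatment stay on the follow-up schedule, telephone or video participation is allowed, and in the compensation table the 3-month visit carries the highest payment for measures ($50).

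The simulated rates place the truth exactly at the margin and use a one-sided 5% test that the SAP does not use. The highest figures need n=80, whereas the SAP describes its sample as small. The analysis is presented as exploratory and post hoc, with no rule for declaring noninferiority, and the follow-up mixed models for PCL-5 and PHQ-9 are said to agree.

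All of this limits the point without removing it. The handling of missing scores is still unstated. The follow-up models are not reported in detail, are not shown for CAPS-5, and give a linear-plus-quadratic curve, not a visit contrast set against the margin.

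**Conclusion.** The point holds in conditional form. Maintenance of gains rests on separate two-visit comparisons made outside the longitudinal model, by an adaptation that is not described. If that adaptation uses complete pairs, and if people who worsen are lost more often, it leans towards noninferiority. If either condition fails, this bias does not arise.

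Under the step 2 to 4 assumptions, a true 5-point worsening appears as roughly 3 to 4.5 points, with false noninferiority of about 7-17% at n=20 and 9-41% at n=80. These figures illustrate direction and rough size for the 3-month comparison; they are not properties of the SAP's Bayes factor. A model-based contrast removes the bias when observed scores explain dropout, and only part of it when unseen relapse does. Given the post hoc status, this is an inexpensive improvement that should be made, not a defect that overturns the analysis.

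**What to change.** - Describe the repeated-measures modification, and state how missing 1-month and 3-month scores were handled.
- For PCL-5, PHQ-9 and CAPS-5, fit a mixed model with visit as a categorical factor to all available post-treatment scores. From its posterior, report the contrasts of 1 month and 3 months with 1-week post, and the probability that each mean change is below the margin (5, 3 and 5 points respectively).
- CAPS-5 has no score between 1-week post and 1 month, so its gain is mainly at 3 months.
- Keep the paired Bayes factor as a sensitivity analysis, with the number of pairs for each outcome and visit.
- Add a sensitivity analysis that shifts missing follow-up scores towards worsening by increasing amounts, and report the shift at which the conclusion changes.

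The cost is a little extra analysis with existing data and software. The downside is that the main estimate then relies on missing-at-random given the observed scores, which is why the last analysis is needed.
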